#### **5.4 Inclusion/Exclusion Criteria**

Veterans who (a) are entering a mental health residential rehabilitation treatment program (MH RRTP) at one of three study sites (Palo Alto, Little Rock, or Bedford VA), and (b) had been arrested and charged and/or released from incarceration in the past 5 years prior to MH RRTP admission will be eligible for participation.

The only exclusion criterion is being too cognitively impaired to understand the informed consent process and other study procedures. Patients will be screened for cognitive impairment using the Montreal Cognitive Assessment’s section on Orientation. For patients who are not able to correctly answer the Orientation (date, location) items, the research assistant will further educate the patient on the purpose of the study and procedures until he or she is able to recall and reflect on these procedures. Patients who are unable to do so will be deemed too cognitively impaired to understand the study’s procedures, participate meaningfully in MRT, and respond to interviews, and therefore will be ineligible (in our past studies of Veterans from MH RRTPs, only 1% of prospective participants was excluded on this basis). For those who are eligible, written informed consent will be obtained, and the baseline assessment will be administered.

#### **5.5 Study Evaluations**

**Baseline assessment.** Research assistants will collect baseline self-report data on sociodemographics (e.g., age, gender, race/ethnicity, marital status, education, and income) and (a) recidivism risk and criminal history; (b) health-related functioning; (c) SUD/mental health treatment and mutual-help history; and (d) mechanisms of MRT. This assessment will be conducted in person at the MH RRTP and will take 60 minutes to complete. We will pre-test the assessment protocol to ensure that it can be completed within this timeframe.

Recidivism risk and criminal history. Recidivism risk will be measured with the Psychological Inventory of Criminal Thinking Styles (PICTS), which consists of 56 items to assess antisocial cognitions and attitudes. These items are summed to create a General Criminal Thinking (GCT) score, which provides an overall index of recidivism risk. Scores on PICTS scores have good internal consistency, and, in the prediction of general recidivism (e.g., rearrests), multiple meta-analyses indicate that the validity of the PICTS GCT score is high and provides incremental prediction of this outcome above and beyond state risk factors such as age and criminal history, as well as interview-based measures of recidivism risk (e.g., Level of Service Inventory).

Data on patients' criminal history, including type and recency of criminal justice involvement, will be obtained from a modified version of the legal section from the Addiction Severity Index (ASI) (i.e., age of first arrest and charge; number of times arrested and charged, number of times incarcerated, and total number of months incarcerated in past 12 months, past 5 years, and lifetime; number of months since most recent criminal justice event; and most recent offense for which the Veteran was arrested, charged, or incarcerated). We will verify the ASI legal section data using the HOMES assessments, which include information on criminal history and are administered to all patients entering VA MH RRTPs, and all patients served by VJP. Based on the empirical literature, patient reports of their criminal history are highly correlated with their criminal records.

Health-related functioning. We will use the ASI to assess substance use, and mental health, housing, and employment status at baseline. In addition to items on housing, the ASI assesses functioning in several problems areas, e.g., alcohol use, drug use, psychiatric, and employment. In each domain, items measure the number, extent, and duration of problems (lifetime and past 30 days). Composite scores are produced from sets of items that are standardized and summed (range from 0 to 1; higher scores indicate poorer outcomes), which provide internally-consistent indices of patient status in the relevant domains in the past 30 days. Prior work supports the validity of self-reports on these areas. To further assess substance use, the Time-Line Follow Back (TLFB) will be administered. The TLFB is a retrospective, calendar-based measure of substance use, which has been validated for administration in-person or via phone and will provide information on quantity and frequency of substance use in the 6 months prior to the baseline assessment (i.e., percent days of use; percent days abstinent; most consecutive days using; most consecutive days abstinent). To further assess psychiatric status, the PHQ-9 will be administered to assess symptoms of major depression, and the PTSD Checklist (DSM-V version) will be used to assess symptoms of PTSD. VA records will be used to gather SUD and mental health diagnoses on patients at the time of admission to the MH RRTP, per ICD-9 codes linked to the appropriate bedsection code in the inpatient files.

SUD/mental health treatment and mutual-help history. We will use the ASI to assess participants' treatment history (i.e., any care [yes/no]; number of visits over the lifetime and past 12 months) for SUD (outpatient, residential, pharmacotherapy) and mental health (outpatient, inpatient, residential). Information on VA health services utilization in the past 12 months will be collected via patient records for these domains of care. Data on non-VA health care utilization will be collected to help determine whether the two condition arms are balanced and ensure that any changes in utilization of VA services are not due to changes in non-VA care. To measure attendance (yes/no; number of meetings) and involvement in mutual-help groups (lifetime, past 12 months) we will use items from the Alcoholics Anonymous Inventory.

MH RRTP completion and SUD/mental health continuing care utilization. MH RRTP completion will be determined from VA administrative databases. Data on SUD/mental health continuing care utilization since the prior assessment will be obtained from (a) VA administrative databases, for VA care; (b) an interview on non-VA health care utilization, for non-VA care; and (c) the Alcoholics Anonymous Inventory for mutual-help group attendance. From these data sources, we will calculate whether SUD/mental health care was received (yes/no) and the amount of care received (number of outpatient visits; number of mutual-help group meetings). To be comprehensive, we will also assess whether SUD or mental health inpatient/residential care occurred since the prior assessment (i.e., any care [yes/no], number of bed days of care).

MRT mechanisms. We will re-administer the measures used at baseline to assess interpersonal functioning and affiliations with antisocial and substance abusing peers.

Measuring utilization of VA health care services. We will collect data on patients' use of VA health care (SUD; mental health) to test our hypothesis (i.e., effects of MRT will be mediated in part by service utilization). National data extracts from the Patient Treatment Files (PTF) and National Patient Care Databases (NPCD) will be used to determine utilization of VA residential (MH RRTP) and outpatient care. Corresponding information on utilization of VA-paid care at non-VA facilities is available in the national Fee Basis files and will be searched for all study participants. These datasets are maintained at VA's Corporate Data Warehouse and available, in SAS format by fiscal year, through

VA's VINCI intranet site. We will obtain all PTF, NPCD, and Fee Basis files for study participants for all health care encounters that occur in a 12-month period prior to, and ending 12 months after, study enrollment. From the PTF files of residential care, we will extract the following data: patient ID (i.e., SCRSSN); station; treating specialty (bedsection); date of service; diagnostic and procedure codes; and length of stay. From the NPCD files of outpatient care, we will extract the following data: patient ID; station; clinic stop code; date of service; and diagnostic and procedure codes. Care identified in the Fee Basis files will be classified by setting and purpose of visit using several variables. Specifically, at each assessment we will ask patients to report on non-VA care, including type, timing, and duration of care.

**Arrest and incarceration records.** We will obtain state and federal arrest and incarceration records. We anticipate that participants will be difficult to reach by phone or through alternate contacts and may have no current information in their VA medical health record. This information is essential to determining if there is a difference between usual care and the MRT group, whether those in the treatment condition have a lower overall recidivism risk

**Fidelity assessments.** To assess ongoing fidelity to the MRT condition, group sessions will be video- and audio-taped (with consent) and evaluated against a Fidelity Checklist by [name] and the other site PIs using the following schedule: (1) the first eight sessions for each IC, which corresponds to the first month of running MRT groups, will be assessed for protocol fidelity and the IC will be provided with corrective feedback; (2) one session for each IC will be reviewed at random each month by the site PI to ensure fidelity to the intervention. [name] will also lead monthly treatment fidelity calls with the site PIs and ICs to (a) maintain adherence to the MRT protocol across sites, and (b) review the results of the de-identified MRT Fidelity Checklists that were completed by site PIs. For ICs who fall below an 80% rating on the checklist, a one-on-one, hour-long consultation with [name] will be triggered to provide corrective feedback to the IC. [name] has a protocol for fidelity drift, which he has used to retrain ICs in his past MRT studies. A follow-up, hour-long consultation with [name] will take place two weeks later to review the IC's progress.

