UC condition. All patients, regardless of condition, will receive usual MH RRTP care at the Palo Alto, Little Rock, and Bedford VAs. At each site, we will recruit from residential treatment programs that serve veterans dealing with homelessness, substance abuse, and/or mental health issues. These MH RRTPs aim to improve Veterans’ health and facilitate community reintegration by providing care (24 hours per day, 7 days per week) using a structured residential environment. The participants’ health care providers at the MH RRTPs (not the study team) will be providing usual care. No standard treatment will be withheld.

MRT condition. Patients assigned to the MRT condition will receive usual care in the MH RRTP plus two hours of MRT weekly, which will begin within a week of entering the MH RRTP in order to complete all sessions during the 3-month program stay. Over the course of 12 weeks, they will attend 24 group sessions (one-hour sessions, twice per week). The overall length of the intervention (12 weeks) corresponds to the national average of bed days of care for Veterans in MH RRTPs (3 months). In FY13, an average of 70% of patients entering the MH RRTPs at the Palo Alto, Little Rock, and Bedford VAs stayed at least 90 days (approximately 13 weeks). Thus, the majority of patients will have full exposure to the 12-week intervention by virtue of staying in the MH RRTP. For the patients who do not stay for 12 weeks, continuing care services are still available at the MH RRTP at each site, and those who have not yet completed the full MRT protocol when they discharge from the MH RRTP will still be able to get full exposure to the intervention as outpatients, and will be encouraged to do so.

The MRT curriculum consists of short assignments, grounded in cognitive-behavioral techniques, which move participants through 12 steps that aim to restructure antisocial cognitions and behaviors. To progress through the steps, patients complete homework between group meetings and at the next group each patient presents his/her homework to the group members for feedback. Participants move through steps at a rate of approximately 1-2 sessions and group sessions can incorporate new members at any time. With open enrollment, patients are presenting on different steps, which is advantageous because those who have progressed farther are able to share their insights to newer patients who are at lower steps. Open

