enrollment is also advantageous as it allows for recruitment of all eligible patients as they enter the MH RRTPs.

The MRT groups will be facilitated by a combination of (a) members of the research team who are already listed in this application, (b) to-be-named (TBN) VJP Specialists from the local facility who are not MH RRTP staff, and (c) TBN staff members of the MH RRTP at each site. To reduce risk of contamination, the TBN staff members from the MH RRTPs will be specifically instructed to not provide the study intervention to any Veterans who were assigned to the usual care condition.

A full dose of MRT is 24 sessions over 12 weeks. To facilitate patients' completion of the full dose, we will (a) remind patients at the end of each MRT session about the treatment schedule and emphasize the importance of full participation; (b) contact patients who miss a session to determine the reasons for the absence and encourage participation in future sessions; (c) offer incentives (e.g., certificates) to patients who complete the full dose – such incentives are highly valued by Veterans as it allows them to demonstrate to court-related decision makers that they complied with treatment; (d) encourage participation in MRT groups as outpatients for those who have not yet completed the full dose when they discharge from the MH RRTP. These efforts notwithstanding, there is evidence that smaller doses of MRT can be effective (i.e., completion of seven steps in the MRT curriculum can lead to long-term positive changes). According to [name] and VJP Specialists who have run MRT groups, a minimum dose for this study is 12 sessions. To maximize clinical usefulness of the data, we will also examine outcomes as a function of dose.

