Examine mechanisms (i.e., reasons MRT is effective). MH RRTP completion (yes/no) and SUD/mental health continuing care utilization (outpatient attendance [yes/no] and amount; mutual-help group attendance [yes/no], number of meetings) will be examined as mediators between condition and risk for recidivism, and between condition and the health-related outcomes at the 6- and 12-month follow-ups. We will conduct regression models that correspond to a hypothesized causal sequence among (1) MRT, (2) one of our hypothesized mediators, and (3) better outcomes. In each model, we will control for relevant covariates (e.g., baseline values for sociodemographics and the dependent variable). In the first regression, a dummy variable representing the MRT intervention will be the independent variable and the dependent variable will be the outcome (e.g., PICTS GCT scores). In the second regression, MRT will be the independent variable and the dependent variable will be the potential mediator. In the third regression, the potential mediator will be the independent variable and the dependent variable will be the outcome. If the coefficient for MRT or a potential mediator is significant in all of these cases, we will proceed. In the final regression, the MRT dummy variable will be entered simultaneously with the potential mediator as predictors of the outcome. If the coefficient for the potential mediator is significant and the coefficient for the MRT dummy variable on the outcome is reduced, we will conclude that mediation is supported and will evaluate whether the indirect effect is significant. To account for variability in intensity of continuing care services, we will test for significant interactions on outcomes between our measures of continuing care and a variable for site.

We will also determine if any significant, direct effects of MRT on (a) overall risk for recidivism, and (b) the health-related outcomes, are mediated by specific mechanisms of MRT (i.e., improvements in interpersonal functioning and reductions in affiliations with antisocial and substance abusing peers). We will conduct GLMM regression models that correspond to a hypothesized causal sequence among (1) MRT (vs. UC), (2) the potential mechanisms, and (3) one of the outcomes, and control for covariates. Finally, we will conduct regression analyses

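### The 6-month continuing-care mediator is counted from the in-residence baseline, and no rule removes care during the index stay or outpatient MRT sessions, so the 6-month test of hypothesis 1c can be biased

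*Combined protocol and SAP*

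**What the plan says.** Section 3.0 states hypothesis 1c: the effects of MRT are mediated in part by completing the MH RRTP and by using SUD and mental health continuing care. Section 5.5 fixes the counting window for the second mediator: "Data on SUD/mental health continuing care utilization since the prior assessment will be obtained from (a) VA administrative databases, for VA care". Non-VA care (by interview) and mutual-help attendance (by questionnaire) follow the same interval. From these sources the plan derives whether any care was received and how much.

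The assessment before the 6-month visit is baseline. Section 5.5 says of it: "This assessment will be conducted in person at the MH RRTP and will take 60 minutes to complete". Section 5.1 places randomisation after baseline and then schedules MRT, "which will begin within a week of entering the MH RRTP in order to complete all sessions during the 3-month program stay". Baseline therefore falls at about admission.

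For MRT patients who leave early, Section 5.1 says they "will still be able to get full exposure to the intervention as outpatients, and will be encouraged to do so". The same section bars usual-care patients from MRT groups.

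Section 5.6 says that programme completion and "SUD/mental health continuing care utilization (outpatient attendance [yes/no] and amount; mutual-help group attendance [yes/no], number of meetings) will be examined as mediators", at both 6 and 12 months. Section 5.5 also records, for completeness, "whether SUD or mental health inpatient/residential care occurred since the prior assessment (i.e., any care [yes/no], number of bed days of care"). That item is not in the Section 5.6 list of mediators.

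Neither section ties the start of the count to discharge, removes visits or meetings dated within the index stay, or removes MRT sessions. The VA extract is likewise anchored on study enrolment.

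**The concern.** Continuing care ordinarily means care after the residential episode, and Section 5.1 uses the term that way for patients who leave before 12 weeks. A count that starts at admission measures something else in its first half. Two problems follow at the 6-month visit.

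First, outpatient visits and mutual-help meetings during the stay are labelled continuing care. A patient who stays longer has more time to accrue them, so the measure partly restates programme completion, which is tested as a separate mediator.

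Second, an MRT patient who finishes the course as an outpatient may generate VA encounters simply by receiving the intervention. If these are coded as SUD or mental health visits, the treatment is counted as its own mediator, and in one arm only.

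Both act on the second regression in Section 5.6, where the mediator is regressed on MRT. A significant coefficient there could reflect the counting rule and not a change in continuing care.

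**Working it through.** **1. The plan's own dose figure.** Two sessions a week × 12 weeks = 24, which agrees with Section 5.1: "A full dose of MRT is 24 sessions over 12 weeks". Twelve weeks is 84 days. Section 5.1 also reports that in FY13 an average of 70% of patients at the three sites "stayed at least 90 days (approximately 13 weeks").

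**2. How much of each window is index stay.** Six months = 365.25/2 = 182.6 days.
- 84-day stay: 84/182.6 = 46%, leaving 98.6 days.
- 90-day stay: 90/182.6 = 49%, leaving 92.6 days.
- If baseline falls a full week after admission, an 84-day stay takes 77/182.6 = 42%.
- Months 6–12: 0% for a stay of this length.

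**3. Outpatient MRT sessions counted as visits.** From the plan: 183 per arm, two-sided alpha .05 (Section 5.6), and 1 − 0.70 = 30% leaving before 90 days. Assumed, because the plan gives no figure:
- Discharge of early leavers is uniform over the 12 weeks, so on average 6 weeks × 2 = 12 sessions remain.
- A share q of early leavers finish as outpatients.
- Every such session is logged as an SUD or mental health visit.
- MRT has no true effect on other care.
- The SD of the visit count is 10 or 20.

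Mean extra visits per MRT patient = 0.30 × q × 12 = 3.6q.

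Chance of a significant result in MRT's favour = Φ(3.6q / (SD × √(2/183)) − 1.96). For q = 0.50 and SD 10: 1.8/1.045 = 1.72, and Φ(−0.24) = 41%.

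For the yes/no mediator, with an assumed usual-care rate of 70%, the MRT-arm rate becomes 0.70 + 0.30 × 0.30q.

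| q | Extra visits | SD 10 | SD 20 | Yes/no |
|---|---|---|---|---|
| 0.10 | 0.36 | 5% | 4% | 4% |
| 0.25 | 0.90 | 14% | 6% | 7% |
| 0.50 | 1.80 | 41% | 14% | 16% |
| 1.00 | 3.60 | 93% | 41% | 51% |

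With no artefact, 2.5% is expected in that direction. This is a normal approximation that ignores the extra variance the sessions themselves add, so the figures show scale only.

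**4. Extreme case.** If MRT sessions during the stay were also logged as outpatient visits (12 to 24 per patient), the same formula gives more than 99.9% at either SD. The plan does not say that they are.

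**5. A force in the other direction.** If only post-discharge care is captured, longer stays leave less time for it. Ten extra days remove 10/98.6 = 10% of the time available by month 6. Between arms, suppose early leavers go at day 30 (152.6 days left) and MRT raises completion from 70% to 80% (both assumed):
- 70%: 0.7 × 92.6 + 0.3 × 152.6 = 110.6 days.
- 80%: 0.8 × 92.6 + 0.2 × 152.6 = 104.6 days.
- Difference: 6.0/110.6, about 5% fewer days. With leavers at day 14 (168.6 days left) the means are 115.4 and 107.8, or 6.6% fewer.

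**The case against.** The term continuing care may already exclude care during the stay, so a sensible analyst would count from discharge without being told. Section 5.1 supports that as the intent. The operational text does not: it asks only whether care was received, and how much, over an interval that opens at baseline.

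The coding of MRT sessions is unknown. Facilitators include research staff and VJP Specialists, and Section 2.0 places VJP under the VA homelessness office, so SUD or mental health coding cannot be presumed. This objection stands, and that part of the point is conditional.

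The artefact touches mainly one link. Section 5.6 also requires MRT to predict the outcome and the mediator to predict the outcome, followed by a joint model and a test of the indirect effect. This stands too. A reader might infer that hypothesis 1c is settled by construction, but the documents do not support that.

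A reader might also infer that the bed days of the index stay enter the mediation test. They do not, because Section 5.6 tests only outpatient visits and mutual-help meetings alongside completion.

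Finally, a reader might compare a day-30 leaver with a 90-day completer (152.6/92.6 = 1.65) and call 65% the bias. That contrasts two patients, whereas the regression contrasts two arms, where step 5 gives about 5%. It also arises only if nothing accrues during the stay, which is not the literal rule.

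On remedy, it can be said that dividing by days at risk turns an amount of care into a rate, a different quantity, and that discharge is a post-randomisation event tied to the other mediator. Both points are fair and limit what the fix should demand.

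**Conclusion.** The point holds as a gap in the definition of one mediator at one visit. Followed literally, the 6-month window is nearly half index stay for a standard 3-month admission. It labels care in residence as continuing care, and it would include MRT itself wherever sessions are logged as SUD or mental health encounters. This can bias the MRT-to-mediator step for hypothesis 1c at 6 months.

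The size cannot be fixed from the documents. It depends on how sessions are coded, how many early leavers finish MRT as outpatients, and how variable visit counts are. The effect of in-stay visits and meetings is not quantified, because the plan gives no rates for them.

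The month 6–12 window is largely unaffected for a standard stay. The definition of programme completion and the primary PICTS comparison are also unaffected. The change should be made before analysis, partly so that the window is not chosen after the data are seen.

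**What to change.** In Sections 5.5 and 5.6:
- Define the 6-month continuing-care mediator as SUD or mental health outpatient visits and mutual-help meetings after discharge from the index MH RRTP stay. The discharge date can probably be derived from the date of service and length of stay already in the residential extract.
- Exclude study MRT sessions from the visit count in both follow-up windows, by matching attendance records to encounter dates or clinic stop codes.
- Ask about mutual-help meetings since discharge, or restrict the meeting mediator to months 6–12, because Section 5.5 plans only attendance and a number of meetings.
- Keep the amount of care as the main mediator. Because post-discharge time will then vary with length of stay, report a visits-per-day version as a sensitivity analysis, not a replacement.

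The cost is wording plus some data programming. Dates of service, stop codes and length of stay are already to be extracted. Sessions attended are needed for the planned dose analysis, though the protocol does not state that attendance is kept by date. Patients still resident at 6 months will have no continuing-care window at that visit.
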